- b. The use of personal mobile phones for the improvement of ART adherence among adolescents living with HIV is feasible and acceptable.
- c. ART adherence among adolescents is predicted by demographic, socioeconomic, and psychosocial factors.

METHODOLOGY

The proposed study is targeted at adolescents living with HIV/AIDS who are on ART but are not adherent to medications. Two hundred participants will be recruited to participate in a randomized controlled trial to evaluate the effectiveness of interactively tailored SMS reminders on the improvement of ART adherence. The study will be conducted in Ogun State in the southwestern part of Nigeria over a 52-week period.

Participants and setting

Nigeria has 36 states in six geo-political zones. The Southwest geopolitical zone is one of the six and consist of six states namely, Ogun, Lagos, Oyo, Osun, Ondo and Ekiti states. The study will be based in Ogun State and extend to the other five states in Southwest Nigeria in order to meet recruitment goals. Ogun State is one of the 36 states in Nigeria. Ogun State has an estimated 161,200 PLHIV living with HIV and an HIV prevalence rate of 3.1%. Thirteen thousand five hundred (13,500) PLHIV are currently accessing antiretroviral drugs across 24 treatment clinics in the State.

Study design and procedure

A single-blind, parallel-design (ratio 1:1), and multi-center RCT of 200 adolescent living with HIV who are non-adherent to medications will be conducted over a one-year period at HIV clinics in Ogun State and other states in Southwest Nigeria. This study is designed to have 80% power to detect a difference of 20%. When the proportion of adolescents who are adherent to ART was taken as 49% (6) and 10% attrition rate, a sample size of 96 per group was obtained using STATA 15/C statistical software. The study will recruit 200 participants from the ART clinics in Southwest Nigeria into a randomized controlled trial (RCT). Convenience sampling method by which participants will be recruited on routine clinic visits across five (5) high patient-density ART sites will be used.

Participants' recruitment

Recruitment of participants will occur over a three-month period. Recruitment will be based on five eligibility criteria namely:

- a. HIV seropositivity
- b. Being on ART for at least six months
- c. Age 15 to 19 years as at last birthday
- d. Use of personal mobile phone
- e. Poor adherence to ART

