For the purpose of this study, we defined poor adherence as self-reported < 95% adherence in the preceding one month using a validated visual analogue scale (25, 26). Self-reported 95% adherence level is an ideal cut-off point because self-reported measures tend to exaggerate adherence and such high adherence level will minimize the occurrence of false-negatives (27). Adolescents who are too ill to require hospital admission will be excluded from the study.

Initial eligibility screening and recruitment will be carried out by the primary caregivers using a checklist. Potential participants who meet the first four criteria will be presented with a visual analogue scale (VAS) labelled 0 to 100% at intervals of 5%. They will be educated on the implication of various percentages e.g. 0%, 50%, and 100%. They will be required to put a mark on the line at the point that shows their best guess about how much of their prescribed ART medication they had taken in the preceding one month (4 weeks). Volunteers who choose points less than 95% mark will be regarded as being non-adherent to ART and will be eligible to participate in the study. Eligible and willing participants will then be referred to the research assistants for a comprehensive informed consent process.

Baseline activities

At the baseline, the research assistants will give the volunteer participants a detailed explanation of the study, including its aim, duration, intervention and possible benefits. All the volunteers will be required to give a signed informed consent in a private room. Adolescents aged 15 to 19 years are thought to be relatively mature. According to a brief of AIDS regulations and Laws in Nigeria, children who are deemed mature in this context are capable of giving informed consent (28). Besides, based on evidence from South Africa and Lesotho, the WHO recommended that the legal age of consent for HIV testing and treatment should be 12 years (29). The consenting volunteers will then be allocated unique identifiers that they will maintain throughout the course of the study. The contact details of the lead investigator will be made available to the participants so that he can be reached directly for any reason that is related to the study. Baseline data will be obtained in a private room by trained research assistants using structured interviewer-administered paper-based questionnaires over a period of about 40 minutes. The questionnaire will assess:

1. Socio-demographic variables.

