ART adherence will be measured at baseline and at every follow-up visit. Complete case analysis and the intention-to-treat analysis will be carried out. Baseline characteristics will be compared using the chi-square test, rank-sum test, and independent t-test as appropriate. The proportion of participants who are adherent to ART [$\geq 95\%$] at the end of the follow-up period will be compared with the baseline data using the chi-square test. The independent t-test will be used to compare the means of ART adherence between the investigation and control groups after each follow-up visit in order to test if the intervention has any effect. The incidence proportion, incidence rate, relative risk, risk difference, and odds ratio will be used to measure the effect. Multiple regression analyses will be used to control for possible confounders. Subgroup analysis will also be undertaken in order to generate further hypotheses. Survival analysis will also be carried out to adjust for

censoring (competing risk and loss to follow-up). Longitudinal data analysis will be carried out to explore the change in response over time.

The acceptability of the SMS will be accessed by the responses given by participants. The proportion of participants who find the method acceptable will be determined.

The feasibility will be determined using the proportion of participants who are deemed to have completed the study (participate fully).

The study will also assess client satisfaction and the possible effect of adherence on mental health status of adolescents. Correlation and linear regression analyses will be used to determine the association between adherence (percent) and mental health status (GHQ 12 measure).

PROJECT ACTIVITIES AND IMPLEMENTATION

Figure 1 shows a synopsis of the intended activities, RCT design the overall flow during the study.

Timeline

Activity	Period (week)
Initial Planning, Procurement, recruitment and training of project staff	1 to 13
Review meetings	Monthly
Recruitment of participants and informed consent	9 to 21
Randomization and baseline activities	22 to 25
Data cleaning, entry and analysis	9 to 52
Follow-up	26 to 45
Report writing and rounding up	45 to 52

Project management/logistics support

Staffing

For effective project implementation and management, the following staff would be required:

Role		% time	Responsibilities
Principal Investigator	1	25%	Oversees entire project, especially its scientific integrity

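### The only test named for the proportion at least 95% adherent is against baseline; no between-arm analysis is tied to the proportion on which the trial was sized

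*Combined protocol and SAP*

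**What the plan says.** **Sizing (Study design and procedure).** The design is 1:1 with 200 participants. "This study is designed to have 80% power to detect a difference of 20" per cent. "When the proportion of adolescents who are adherent to ART was taken as 49" per cent, with 10% attrition, "a sample size of 96 per group was obtained using STATA 15/C statistical software".

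**Eligibility (Participants' recruitment).** Entry depends on a screening visual analogue scale (VAS): "Volunteers who choose points less than 95% mark will be regarded as being non-adherent to ART".

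**Analysis (Statistical Methods).** Being adherent is defined as 95% or more. The proportion adherent "at the end of the follow-up period will be compared with the baseline data using the chi-square test". A separate sentence gives an independent t-test on mean adherence "between the investigation and control groups after each follow-up visit in order to test if the intervention has any effect". The plan then states that incidence proportion, incidence rate, "relative risk, risk difference, and odds ratio will be used to measure the effect". On analysis sets: "Complete case analysis and the intention-to-treat analysis will be carried out". The regression, survival and longitudinal analyses name no outcome variable.

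**Care in both arms (Intervention; Follow-up; Ethical consideration).** All participants receive adherence counselling at each visit, appointment reminders by SMS, a WhatsApp group and a clinic-based psychological intervention. Only the daily adherence SMS differs between arms.

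**The concern.** The first objective is the effect of the SMS reminders, which only a comparison of the randomised arms can answer. For the outcome behind the sample size, the named test compares two time points instead.

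- Participants are selected for reporting less than 95%, so some rise is expected from regression to the mean.
- Both arms receive substantial support, so adherence may improve with no contribution from the daily SMS.
- An ordinary chi-square would also treat two measurements on the same person as independent. The plan does not say which form it means.

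A significant rise from baseline could therefore be reported on the sizing outcome and say nothing about the intervention. Meanwhile the stated 80% power would belong to a comparison that no named test carries out.

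**Working it through.** **Inputs.** From the plan: 49% adherent, a difference of 20% (read as 20 points, so 49% versus 69%), 80% power, 10% attrition, 96 per group, 200 in total. The plan does not state alpha; I assume two-sided 5%. It gives no expected end-of-follow-up rate under no SMS effect, so those rates are assumptions shown over a range. Arms of 100 are assumed, although simple randomisation may not give exactly that.

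**1. What the sample size belongs to.** For two independent proportions:

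n = [1.960·√(2·0.59·0.41) + 0.842·√(0.49·0.51 + 0.69·0.31)]² / 0.20² = (1.363 + 0.573)² / 0.04 = 93.7, so 94 per group before attrition, and 94/0.9 = 105 after it.

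The stated 96 is close to 94 but is not an exact match. It fits a two-group comparison of proportions with a 20-point difference. A 20% relative increase (to 58.8%) would need 405 per group before attrition.

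**2. Power of the between-arm chi-square, 49% versus 69%** (exact binomial enumeration, uncorrected Pearson):

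| Evaluable per arm | Power |
|---|---|
| 86 (96 less 10%) | 77% |
| 90 (100 less 10%) | 79% |
| 96 | 81% |
| 100 | 83% |

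**3. The named before-after test, starting at 0%.** With 0 of n adherent at baseline and a of n at the end, Pearson's statistic is 2n·a/(2n − a). At n = 90, a = 4 gives 180·4/176 = 4.09, above 3.84, while a = 3 gives 3.05. Four people are enough. With the Yates correction the statistic is 2n(a − 1)²/[a(2n − a)], and a = 6 is needed (4.31, against 3.29 for a = 5).

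The rejection rate at n = 90 is the binomial probability of reaching that count:

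| Assumed end rate | Pearson, P(X ≥ 4) | Yates, P(X ≥ 6) |
|---|---|---|
| 5% | 66% | 29% |
| 10% | 98% | 90% |

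Pooling both arms (n = 180) raises the Pearson figures to 98% and above 99.9%. McNemar's test from a 0% baseline has the same thresholds: 4 uncorrected (p = 0.046), 6 with continuity correction (p = 0.041) or exact (p = 0.031). Pairing alone does not cure the problem; the contrast is at fault.

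**4. Starting above 0%.** The proportion is 0% by design only on the screening VAS. Adherence is assessed again at baseline by several measures, and the Timeline puts recruitment in weeks 9 to 21 and baseline in weeks 22 to 25. From a 10% baseline, n = 90, time points treated as independent:

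| Assumed end rate | Pearson | Yates |
|---|---|---|
| 10% | 5% | 2% |
| 20% | 47% | 39% |
| 30% | 93% | 91% |

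For 10% to 20%, McNemar's test rejects 48% of the time if the time points are independent, 59% if half of the baseline adherers stay adherent, and 98% if all do.

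**5. The between-arm test when SMS does nothing.** With a common rate of 10%, 20%, 30% or 49% in both arms and 90 or 100 per arm, the chi-square rejects 4.5% to 5.6% of the time, whatever rise both arms share.

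**The case against.** The strongest reply is that the plan already contains a randomised comparison. The t-test on means is the analysis designated to test the intervention, intention-to-treat is planned, and the before-after sentence is not described as a test of efficacy. Relative risk, risk difference and odds ratio need a binary outcome, and the only binary adherence outcome defined in that section is the 95% cut-off. On this reading only the drafting is loose.

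Much of this stands. The trial does not lack a between-arm analysis, the effect measures most naturally mean between-arm measures, and the rejection rates above are those of the before-after test, not the trial's false-positive rate for SMS. But the effect-measure sentence gives no outcome, cut-off, time point, test or interval, and the plan lists five adherence measures and five follow-up visits. The t-test concerns means, which the trial was not sized on.

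A second objection is that the sizing sentence does not repeat the 95% cut-off, and the Background gives 49% as a viral suppression rate. That is true, so the link is by the plan's own terms: the sizing paragraph uses 49% as the proportion adherent, and Statistical Methods defines adherent as 95% or more.

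**Conclusion.** The concern holds and should be fixed. As written, the only test named for the proportion at least 95% adherent ignores randomisation, and no stated between-arm analysis is tied to that proportion. The named test can reject often with no SMS effect: 66% to 98% of the time from 0% to end rates of 5% to 10%, and 47% from 10% to 20%, at n = 90 without continuity correction. The between-arm test that the sample size implies has about 77% to 81% power across 86 to 96 evaluable per arm.

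The result rests on two-sided 5%, a 20-point difference, and assumed end rates. The direction of the conclusion does not depend on those rates, because a contrast with baseline cannot isolate the SMS at any of them. The defect is limited to this proportion; the between-arm t-test on means is unaffected.

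**What to change.** Replace the chi-square sentence in Statistical Methods with wording such as:

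> The proportion of participants with ≥95% adherence at week 20 will be compared between the intervention and control groups as randomised, by chi-square test with the risk difference and 95% CI. The relative risk and odds ratio refer to this same contrast. Change from baseline within each group will be described without a p-value.

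The t-test on means can stay as written. Before the coded group list goes to the analysts, two decisions should be recorded: which of the five adherence measures defines this proportion (the VAS is the one that defines eligibility), and how missing week-20 data are handled.

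The cost is a few sentences and those two decisions, with no new data or visits. The missing-data rule is the sponsor's choice, but its effect on power should be stated. Suppose 100 are randomised per arm, with 49% versus 69% among those observed. At 10% missing, counting missing as not adherent gives 0.9 × 49% = 44.1% versus 0.9 × 69% = 62.1%.

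| Missing per arm | Power, missing counted as not adherent | Power, complete cases |
|---|---|---|
| 5% | 79% | 80% |
| 10% | 74% | 79% |
| 20% | 64% | 73% |

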2. HIV/AIDS risk behaviour assessment: This will be done using the AIDS Risk Behavior Assessment (ARBA); a validated, adolescent-specific tool for the assessment of sexual behaviour, drug and alcohol use, and HIV-associated needle use. It assesses sexual behaviour over the previous 30 days and the previous three months (30).
3. Alcohol and Drug abuse assessment: The Alcohol Use Disorders Identification Test (AUDIT) will be used to assess alcohol abuse. AUDIT, which was developed in 1982 by the World Health Organization, is a simple tool that is used to screen for and to identify people who are at risk of alcohol problems (31). The drug abuse screening test (DAST-20, adolescent version) will be used to screen for drug abuse. DAST is a validated scale that was designed to provide a brief, self-reported instrument for population screening, clinical case finding, and treatment evaluation research. It yields a quantitative index of the drug abuse consequences (32, 33).
4. Client Satisfaction Survey: A 22-item adaptation of the SERVQUAL tool will be used for this purpose. First published in 1988, the SERVQUAL is a multi-dimensional tool that assesses patients expected and perceived quality of services across five domains. Its use currently dominates research and industry for the assessment of quality of services and is well-validated in HIV service quality assessment (34).
5. Adherence assessment: This will be done using the validated visual analogue scale (described above), Viral load assessment, monthly pill count, pharmacy records and the AIDS Clinical Trials Group (ACTG) adherence questionnaire (35). The research assistants will carry out pill counts and obtain the pharmacy records. Adherence assessment will be carried out at baseline and at every follow-up visit.

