All the participants will be enrolled into a "whatsapp" group where they will discuss satisfaction with ART services provided to them. An expert will be involved on the group to offer counsel on issues of client satisfaction with ART services. All the participants will also receive a simple clinic-based intervention that is based on stress and coping theories and cognitive behavioural therapy which is aimed at improving their mental status.

Follow-up

The follow-up visits will hold every four weeks at 4, 8, 12, 16, and 20 weeks after the baseline to coincide with the participants' routine clinic visits. ART adherence and client satisfaction will be assessed at each follow-up visit. The participants will also receive the adherence counseling by trained counselors at each visit. CHIV viral load assessments will be done at Baseline and 20 weeks. In order to complete the study, a participant is required to attend all follow-up visits.

[figure not shown]

Figure 1: Randomized controlled study design

Adherence counseling

In this trial, the counselors will be female master's degree level social workers with ART counseling experience. The adherence counselor will be mentored and will be supervised by the investigators. Adherence counseling will be conducted in a setting that mimics a typical ART clinic setting. Each session will consist of a 15 minutes face to face session and will deliver information on the impact of HIV on the

human immune system, the role of ART, the importance of adherence, the characteristics and consequences of non-adherence, and strategies to enhance adherence. The '5As of adherence' approach will be used (38).

Trial Assistance

The trial assistants will be bachelor's degree holders in relevant disciplines and with relevant research experience. They will be trained in research ethics, the study protocol, data collection tools, and data entry. They will obtain a signed informed consent from participants and allocate unique identifiers to them. The trial assistants will also administer the questionnaires, enter data into analysis software and assist participants in getting laboratory investigations done.

Trial Coordination

This trial will be coordinated on a day-to-day basis by a coordinator who will be an MPH degree holder with relevant experience in research coordination.

EXPECTED OUTCOMES

Primary outcome measure (ART adherence)

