ART adherence will be assessed using the visual analog scale (VAS), Viral load, Pill count, Pharmacy record, and the AIDS Clinical Trials Group (ACTG) adherence questionnaires at baseline and during every follow-up visits. The VAS has been found to be reliable, valid and suited for patients in resource-limited settings with insufficient human resources for time-consuming adherence assessments. It showed the highest sensitivity to detect patients with possible virologic failure at 95% cut-off for non-adherence (1, 39).

Secondary outcome measures

1. Patient satisfaction

Patient satisfaction is a potent predictor of ART adherence (40, 41).

2. Mental health status

Mental illnesses are varied, especially among adolescents because they experience a range of emotional, social and physical changes. The effects of mental illnesses on adolescents vary and can be acute, chronic, mild or severe. The commonest mental illnesses among adolescents are depression and anxiety disorders. Adolescents living with HIV have additional risk factors that increase their susceptibility to mental illnesses. This increased vulnerability may result from the loss of family, having to live independently, with relatives or in care. They are often exposed to poverty and violence. The stigma, discrimination, and social isolation that is associated with HIV further impact mental health negatively. They may result in poor adherence to ART (8).

The General Health Questionnaire (GHQ) 12 will be used to assess the mental health status in this study. The GHQ which was developed in 1970 by Goldberg to measure the current mental health has since been used in different settings and different cultures (42). The questionnaire was originally developed as a 60-item instrument but many shorter versions have been developed over time. The GHQ-12 is brief, simple, easy to complete, and has been widely used in research settings as a screening tool. It is a consistent and reliable instrument when used in the general population (42, 43).

Process measures

An ART adherence checklist will be completed by the counselors during each counseling session. The filled checklists will be examined to monitor the adequacy of counseling sessions. The participants will be required to send a reply SMS as soon as possible after ART and follow-up reminders are received. This will help confirm that SMS are delivered to participants and serve as a measure of feasibility and acceptability of the intervention.

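### The test of effect is an unadjusted t-test at each visit; baseline adherence, which everyone has, is not pre-specified as a covariate in any planned model

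*Combined protocol and SAP*

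**What the plan says.** The Statistical Methods section states: "The independent t-test will be used to compare the means of ART adherence between the investigation and control groups after each follow-up visit". The sentence goes on to give the purpose as testing for an effect of the intervention, a purpose given to no other between-arm test.

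Two analyses in the same section could carry adjustment. One is regression: "Multiple regression analyses will be used to control for possible confounders". The other is longitudinal: "Longitudinal data analysis will be carried out to explore the change in response over time". Neither lists a covariate, a model form or a status relative to the t-test. The chi-square test there sets the final adherent proportion against baseline data, which is not covariate adjustment.

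The baseline value exists for everyone. Item 5 under Baseline activities says "Adherence assessment will be carried out at baseline and at every follow-up visit", and the visual analogue scale (VAS) is also the entry screen: "Volunteers who choose points less than 95% mark will be regarded as being non-adherent to ART".

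The section on the primary outcome measure lists several instruments: "ART adherence will be assessed using the visual analog scale (VAS), Viral load, Pill count, Pharmacy record", and also the ACTG questionnaire. The Statistical Methods section does not say which of these five supplies the mean to be tested.

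**The concern.** When the outcome is measured before randomisation and again afterwards, the baseline value is usually among the best available predictors of the follow-up value. A comparison that ignores it leaves explainable variation in the error term. The t-test remains unbiased under randomisation, and its standard error already allows for chance baseline imbalance. The cost is therefore precision, not validity.

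The second cost is analytic freedom. With covariates unnamed and no adjusted model designated, the adjusted estimate can take many forms, and a reader cannot tell which was planned. The section also plans tests of baseline characteristics between arms, without saying that their results will not drive the choice of covariates.

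**Working it through.** **The plan's own figure.** Study design and procedure says "This study is designed to have 80% power to detect a difference of 20" per cent, from 49% adherent, with 10% attrition and 96 per group. Taking 49% v 69% and two-sided 5% (alpha and sidedness are not stated), the usual formula gives 94 per group before attrition and 105 after, so 96 is not reproduced with all stated inputs on that reading. That calculation concerns a binary endpoint and does not bear on the choice of model. It is noted only because the figures below are not the power of that design.

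**Inputs.** 200 recruited at 1:1 is 100 per arm; after 10% attrition, 90 per arm. Two-sided 5% is assumed. The correlation r between baseline and follow-up adherence is not in the documents and is varied.

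**Step 1: continuous outcome.** Adjustment multiplies the residual variance by 1 − r². A standardised difference d therefore becomes d/√(1 − r²), and the effective sample size becomes 90/(1 − r²). By the noncentral t, d = 0.42 gives the unadjusted test 80.0% power. For example, at r = 0.5: 0.42/√0.75 = 0.485 and 90/0.75 = 120.

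| r | Variance reduction | Effective n per arm | Power |
|---|---|---|---|
| 0 | 0% | 90 | 80.0% |
| 0.1 | 1% | 90.9 | 80.4% |
| 0.2 | 4% | 93.8 | 81.6% |
| 0.3 | 9% | 98.9 | 83.6% |
| 0.5 | 25% | 120 | 89.9% |

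**Step 2: restricted entry.** Enrolling only those below 95% narrows the baseline range and can lower r. As an illustration, take a normal baseline and enrol its lowest 51% (1 − 0.49, an assumption). The cut is at a = 0.025 SD. With λ = φ(a)/0.51 = 0.3988/0.51 = 0.782, the variance ratio is u = 1 − aλ − λ² = 1 − 0.020 − 0.612, or about 0.369. The correlation among those enrolled is r√u/√(r²u + 1 − r²).

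| Unselected r | r among enrolled | Power |
|---|---|---|
| 0.3 | 0.19 | 81% |
| 0.5 | 0.33 | 84% |
| 0.6 | 0.41 | 87% |

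If the lowest 80% were enrolled instead, u is about 0.58. An unselected r of 0.3, 0.5 or 0.6 then becomes about 0.23, 0.40 or 0.50, with power of about 82%, 86% or 90%.

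**Step 3: binary endpoint, 49% v 69%, 90 per arm.** Under a latent-normal model with baseline z and latent correlation ρ, P(adherent | z) = Φ((c + ρz)/√(1 − ρ²)), where Φ(c) is the arm's proportion. The unadjusted variance of the risk difference is (0.49 × 0.51 + 0.69 × 0.31)/90 = 0.00515. The variance of the risk difference standardised over z, divided by this, is 0.976, 0.945 and 0.846 at ρ = 0.2, 0.3 and 0.5. These are reductions of about 2%, 5% and 15%.

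**The case against.** The strongest reply is that this is a preference for efficiency. No bias or inflated type I error is alleged, and the planned regression or longitudinal analysis could well include baseline adherence. That is accurate. The defect is that inclusion is not written down and the adjusted model is not the test of effect.

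It can also be said that the t-test is only one of several unranked analyses: the next sentence offers relative risk, risk difference and odds ratio as effect measures, and the trial is sized on a proportion. This stands in part. The plan does not rank its analyses, and naming one measure has to come first. But those are effect measures, and the t-test is still the only comparison whose stated purpose is to test the effect.

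The size is assumed throughout. The 49% comes from a reference on viral suppression, so 51% is not a documented share reporting below 95% on the VAS, and a normal baseline is doubtful for a scale marked in 5% steps. This also stands, and it limits the second step to an illustration. Enrolling a larger share makes the assumed gain larger, as the 80% case shows.

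The screening VAS and the baseline VAS may be separate readings, since the Timeline puts recruitment in weeks 9 to 21 and baseline activities in weeks 22 to 25. If so, some baseline values could be 95% or above. The continuous baseline value is the right covariate in either case.

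Analysts receive two unlabelled groups. That hides the direction of effect, but not how the size and p-value of the difference change with the covariates chosen.

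**Conclusion.** The concern holds. The stated test of effect is unadjusted, and no planned model pre-specifies baseline adherence. The t-test is valid, so this does not undermine the trial, but the plan should be changed because a better method is available on data already collected.

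The gain cannot be fixed from the documents. With 90 per arm, two-sided 5% and 80% unadjusted power, all used as assumptions, it runs from under half a percentage point of power at r = 0.1 to about 10 points at r = 0.5. Restricted entry makes the lower part of that range plausible. For the binary endpoint the variance reduction is about 2% to 15% over latent correlations of 0.2 to 0.5. Fixing the content and status of the adjusted analysis in advance is worthwhile whatever r proves to be.

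**What to change.** 1. Name one adherence measure taken at every visit, for example the VAS percentage. Viral load cannot serve, because the Follow-up section says "viral load assessments will be done at Baseline and 20 weeks".
2. Make the test of effect one linear mixed model on weeks 4 to 20 with arm, visit, arm-by-visit, the continuous baseline value of that measure, and site. The week-20 contrast is the effect. Baseline adherence is the essential term; site is a reasonable addition because recruitment runs across five clinics under simple randomisation.
3. For the endpoint of at least 95% adherence, compare arms at week 20 by regression on arm, continuous baseline VAS and site, reported as an adjusted risk difference. A baseline split at 95% would carry no information if the screening reading is used, since everyone is below it at entry.
4. State whether the screening or the baseline-visit VAS reading is the covariate.
5. Keep the unadjusted t-test as a supporting analysis.
6. Present baseline characteristics by arm descriptively, and state that baseline p-values will not be used to choose covariates.

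The cost is analysis-plan wording only. Baseline and visit-level adherence are already collected, site is known from recruitment, and the stated software fits these models. The change should be made before allocation is revealed to the analysts in any form.
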